Primary Outcome	Rate of space closure	Digital scanned dental models	
- Scanned digital models in (mm)
○ Models taken every month○ Analysed using 3 Shape Software

Secondary Outcome	Anchorage loss	Digital scanned dental models	Linear measurement in scanned digital models (mm)
	Molar Rotation	Digital scanned dental models	Degrees
	Vertical position	Lateral Cephalometric Xray	Mm
	Torque of anterior teeth	Lateral Cephalometric Xray	Degrees
	Pain	Pain scoring sheets given to patients	VAS scoring from 1-10 ^(Fig 1)

B-Research question:

In orthodontic patients with maxillary protrusion, can frictionless mechanics offer a faster rate of retraction compared to frictional mechanics?

Objectives of the study

Research hypothesis:

The null hypothesis (H_0) of this research is that there's no difference between both frictionless and friction mechanics on rate of retraction during en-masse retraction following 1st premolar extraction.

Primary objective:

Evaluating the rate of En-masse retraction using frictionless vs friction mechanics.

Secondary objectives:

Assessing the amount of anchorage loss, root resorption, pain and discomfort during retraction. In addition to this, changes in vertical position (extrusion/ intrusion), tip and torque of anterior teeth will be measured following en-masse retraction using frictionless vs friction mechanics.

Study design:

This is a randomized clinical trial with two arms parallel group, and 1:1 allocation ratio. In one group, frictionless mechanics will be applied during en-masse retraction, while the other group will receive frictional mechanics. The rate of retraction will then be compared between both interventions.

Material and Methods

I) Participants, Interventions, and Outcomes

A] Study Setting:

The study will be performed in the clinic of the Orthodontic Department at the Faculty of Oral and Dental Medicine, Future University. The recruited sample would be from the Egyptian urban and rural population.

B] Eligibility criteria:

- Inclusion criteria:** for the participants include the following:
 1. Adults and Adolescent patients (both genders)
 2. Age range (14-24)
 3. Patients with maxillary protrusion requiring first premolars extraction (Bimaxillary Protrusion or Class II division 1 cases).
 4. Patients with fully erupted permanent teeth (not necessarily including the third molar).
 5. Cases requiring maximum anchorage during retraction.

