Our sample size calculation is based on a previous study comparing the effect of friction and frictionless mechanics²⁴. Using PS software output, we are planning a study of a continuous response variable from independent Group I and Group II subjects with 1 Group I(s) per Group II subject. In a previous study the response within each subject group was normally distributed with standard deviation 0.76. If the true difference in the Group II and Group I means is 1.0, we will need to study 10 Group II subjects and 10 Group I subjects to be able to reject the null hypothesis that the population means of the Group II and Group I are equal with probability (power) 0.8. The Type I error probability associated with this test of this null hypothesis is 0.05. Considering drop out a sample size 15 per group is appropriate.

F] Recruitment strategy:

The principal investigator will recruit the patients from the clinic of Orthodontic department, Faculty of Oral and Dental Medicine - Future University.

Screening of patients will continue until the total number of participants for the study is collected.

II) Assignment of interventions:

A] Sequence generation:

The supervisor of the study will apply Computer generated random numbers to randomly assign patients to group A (Frictionless) or B (friction) using Microsoft Office Excel 2007 sheet. The patient numbers will be written in the first column, and the supervisor will select function RAND() to generate the randomization number in the second column. These numbers will be sorted according to the randomization number so the first column numbers will be randomly distributed.

B] Allocation concealment mechanism:

The supervisor of the study will write the randomization numbers of the patients on opaque white papers folded three times to form sealed envelopes and store it inside a box. The codes for randomization will be securely held at the secretary's office.

C] Implementation:

At the time of intervention, the main operator will send the patient to the secretary's office. Then, the assigned employee will open the box and ask the patient to select one envelope. The main operator will assign each participant for the corresponding intervention either (friction or frictionless group) according to the list of codes of randomization.

Assignment to either intervention will occur before levelling and alignment stage.

D] Blinding:

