Data will include all photographs, models, radiographs and filled questionnaire.

C] Statistical Analysis:

- The principle investigator will be responsible for the extraction of the required data from the CBCT taken before and after retraction as well as the study models taken at every follow up visit. The data will be sent to a specialized statistician.
- The specialized statistician will be responsible for the statistical analysis of the study by:

1. Presenting the data as mean, standard deviation (SD) and Standard error (SE) values.
2. Using Paired t-test to compare between the friction and the frictionless group of retraction as well as to compare between the pre-and post -treatment data for each group.
3. Using Anova test to determine the rate of anterior segment retraction.

4. Statistically evaluate the patient acceptance for both techniques.

- For this study, the specialized statistician will use IBM11 SPSS12 Statistics Version 20 for Windows to perform the required statistics.
- The significance level will be $P \leq 0.05$. Highly significant variables are detected when P value is less than 0.01.

Assessors Reliability:

- To achieve high reliability for measurements, the supervisor will choose a well-experienced inter-examiner during the study.
- A training session will be provided for the examiners to ensure standard measurements techniques.
- Each examiner will complete the measurements on a model and will repeat the procedure after one week to assess the intra- and inter-examiner reliability.
- The supervisor will compare the measurements of the two assessors for disagreement with a difference of more than one millimeter.
- the supervisor will evaluate the amount of variation in measurements among and between examiners to test the performance of each assessor.
- The examiner with less reliability will receive additional training but will be replaced during the study.
- The specialized statistician will calibrate the intra and inter-examiner reliability for the measurements of the study by the Intra-class correlation coefficient (ICC). The closer the ICC to 1.0, the higher reliability between assessors. According to Fleiss: "ICC values between 0.7 and 0.9 represent good reliability." The kappa scores between study examiners will be calculated, a range of 0.60-0.80 will represent acceptable reliability.

IV) Method Monitoring:

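### The only test the plan assigns to friction versus frictionless is a paired t-test, but the arms are independent, unmatched patients and no pairing rule exists

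*Combined protocol and SAP*

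**What the plan says.** Section III) C] Statistical Analysis lists four items.

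- Item 1 is descriptive.
- Item 2 gives one test two jobs: "Using Paired t-test to compare between the friction and the frictionless group of retraction", and then "as well as to compare between the pre-and post -treatment data for each group".
- Item 3 reads "Using Anova test to determine the rate of anterior segment retraction". It names no factor, no repeated-measures structure and no contrast between arms.
- Item 4 reads "Statistically evaluate the patient acceptance for both techniques" and names no test.

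No independent-samples test appears anywhere in the document.

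The design is stated under Study design: "This is a randomized clinical trial with two arms parallel group, and 1:1 allocation ratio". The sample size section assumes "a continuous response variable from independent Group I and Group II subjects", arrives at 10 per group, and then adds "Considering drop out a sample size 15 per group is appropriate". Under Assignment of interventions, individual patients are ordered by a spreadsheet random number and each draws one envelope for one intervention. Matching, crossover and split-mouth allocation are not mentioned.

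**The concern.** A paired t-test analyses within-pair differences. It suits the second half of item 2, where the same patient is measured before and after. It does not suit the first half, where the two measurements come from unrelated patients.

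Three things follow.

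- **The p-value is not unique.** It depends on an arbitrary alignment of patients. In practice that would probably be the row order of the data sheet, which the plan does not fix.
- **Patients can be lost.** If the arms finish with unequal numbers, anyone without a partner falls out of the analysis.
- **Analysis and sample size disagree.** The stated power of 0.8 belongs to an independent-groups comparison.

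The reach goes beyond the primary outcome. Section I) D] defines all outcomes as T0 to T1 differences, so item 2 is also the only stated arm comparison for anchorage loss, molar rotation, torque and vertical position.

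**Working it through.** **Inputs (sample size section):** difference 1.0, within-group SD 0.76, alpha 0.05, power 0.8, 10 per group raised to 15 for drop-out. Assumptions made here: a two-sided test (sidedness is not stated) and zero correlation between arbitrarily paired patients.

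**1. Reproduce the plan's figure.** For two independent groups, n = 2(1.960 + 0.842)² × 0.76² / 1.0² = 9.07, rounded up to 10 per group. This matches. Reading 0.76 as the SD of paired differences would give 7 pairs, so the plan's calculation is the independent-groups one.

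**2. Power of each test.** Independent test: noncentrality 1.0 / [0.76 √(1/n₁ + 1/n₂)], df = n₁ + n₂ − 2. Paired test with m unrelated pairs: noncentrality 1.0 / [0.76 √(2/m)], df = m − 1, where m is the smaller arm.

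| Completers | Independent: noncentrality, df, power | Paired: noncentrality, df, power |
|---|---|---|
| 10 v 10 | 2.942, 18, 0.795 | 2.942, 9, 0.745 |
| 15 v 15 | 3.603, 28, 0.935 | 3.603, 14, 0.917 |
| 13 v 12 | 3.287, 23, 0.882 | 3.223, 11, 0.835 |
| 15 v 12 | 3.397, 25, 0.904 | 3.223, 11, 0.835 |
| 15 v 11 | 3.315, 24, 0.889 | 3.086, 10, 0.794 |
| 15 v 10 | 3.223, 23, 0.870 | 2.942, 9, 0.745 |

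With equal arms the noncentrality is the same and the loss comes only from the halved degrees of freedom (critical t 2.101 v 2.262 at 10 per arm; 2.048 v 2.145 at 15). With unequal arms, unpartnered patients are lost as well. The unequal splits are assumptions, since the plan gives none.

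**3. Dependence on the pairing.** Re-pairing leaves the mean difference alone and changes only r, the chance correlation between the two columns. With both sample SDs at 0.76, paired t = d / [0.76 √(2(1 − r)/n)]. Take n = 15 and d = 0.571:

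- Independent test: t = 2.058 on 28 df, p = 0.049.
- Paired, r = 0: t = 2.058 on 14 df, p = 0.059.
- Paired, r = 0.5: t = 2.058/√0.5 = 2.910, p = 0.011.
- Paired, r = −0.5: t = 2.058/√1.5 = 1.680, p = 0.115.

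Simulation (200 datasets, 5,000 random pairings each) gives these median 2.5 to 97.5 percentiles of the paired p:

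| n per arm | Difference | Independent p | Paired p over re-pairings |
|---|---|---|---|
| 15 | 0.571 | 0.049 | 0.011 to 0.117 |
| 15 | 1.0 | 0.0012 | 0.0001 to 0.011 |
| 10 | 1.0 | 0.0087 | 0.0009 to 0.047 |

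**4. Error rate and disagreement.** In 400,000 simulated trials with outcome-blind pairing, the paired test's type I error was 0.049 (n = 10) and 0.051 (n = 15). The two tests fell on opposite sides of 0.05 in 9.4% (n = 10) and 3.4% (n = 15) of trials at the planned effect, and in 3.0% and 2.4% when there was no difference.

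**The case against.** **Item 3 may be the primary analysis.** It is the line that mentions the retraction rate, and with monthly models an ANOVA including arm could have been intended. The text does not say so. If it was intended, the plan has two tests for its main question and no rule for which decides. So the point adds to the ambiguity and does not remove it.

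**This may be a drafting slip.** That is plausible: two comparisons share one test name that fits the second, and a competent statistician might simply use the independent test. But nothing in the document corrects the wording, and the change would then be an unrecorded departure made once data are in hand.

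**The practical harm is small.** This largely stands. Type I error is preserved. With 15 completers per arm, paired power is still 0.917. At the planned effect no re-pairing crossed 0.05 with 15 per arm, and only about 1.4% did with 10. The 0.011 to 0.117 range comes from data set at p = 0.049; it shows that the result is not unique, not what typically happens. An even loss such as 13 v 12 keeps paired power at 0.835.

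**The inputs are uncertain.** This also stands. The 0.76 and 1.0 carry no unit and are not said to describe a retraction rate, so the power figures illustrate the plan's own calculation and may not carry over to the primary outcome.

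**Conclusion.** The concern holds. The between-arm test in item 2 is wrong for this design as written; it is not merely under-described. It cannot be carried out without a pairing choice that the plan does not make, and near the significance boundary that choice can decide the result.

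The damage is to the uniqueness of the answer and to the use of all randomised patients. False-positive risk is not inflated, provided pairing is blind to outcome. Power falls by about 0.05 with 10 per arm and 0.02 with 15, and by up to 0.125 (0.870 to 0.745) in the assumed 15 v 10 case. These sizes rest on a two-sided test, uncorrelated pairs and the plan's 1.0 and 0.76. The mismatch between test and design rests on none of them. It must be fixed because it affects the only test assigned to the trial's main question.

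**What to change.** - **Item 2, between arms:** replace the paired t-test with a two-sided independent-samples t-test on one retraction rate per patient, named as the primary comparison and reported as a mean difference with 95% CI. Welch's version is a sensible default; Student's would also match the design. Use the independent test for the arm comparison of the other continuous T0 to T1 outcomes too.
- **Item 2, within arms:** keep the paired t-test for the T0 to T1 change only.
- **Item 3:** state the ANOVA's factors and role, for example describing month-by-month movement, and say that it does not decide the arm comparison. A model with arm between patients and month within patients would also be valid as the primary analysis, but then it must be named as such in place of the t-test.
- **Definition:** say how one rate per patient is derived from the monthly models, since the plan does not.

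The cost is a few lines of wording through the plan's own amendment route. No new data are needed and the sample size stays as it is: simulated Welch power at the planned difference is 0.791 with 10 per arm and 0.935 with 15. The test is standard in the named software.

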Ziegler and Ingervall (1989)²³ conducted a clinical study where the efficiency of maxillary canine retraction was observed by means of sliding mechanics along an 0.018-inch labial arch and an powerchain (AlastiK chain) compared to the use of retraction springs (frictionless mechanics) by Gjessing. Twenty-one subjects were included in the study where the upper first premolars were extracted. It was shown that the canine was retracted faster and with less distal tipping through frictionless mechanics than with the sliding mechanics. The canine retraction spring (Gjessing Spring) was not

superior to the sliding mechanics in controlling canine rotation during the retraction. However, this disadvantage is outweighed by the fact that the correction of rotation after the retraction is less time-consuming than the up-righting of a tipped canine

Dincer et al (2000)²⁴ evaluated the effect of application of Poul Gjessing (PG) Spring for retraction of upper incisors on the dento-alveolar structure compared to the effect of closed coil spring. 63 subjects with angle Class I or Class II were selected and divided into two groups, the PG group with 17 subjects and the closed coil spring group with 19 subjects. They concluded that mesial movement of buccal segment and distal movement of root apex of incisors were accompanied with the incisor retraction in both groups. Moreover, a significant incisors intrusion in PG group and a significant increase in deep bite in coil spring group. Plus, the PG spring produced three-dimensional control in the movement of upper incisors, so that application of additional intrusive mechanics after completion of the incisor retraction became unnecessary.

2) Lateral Cephalometric for measurement and its reliability

Ellis and McNamara (1986)²⁵ evaluated seventeen measurements of incisor angulation and position for their applicability in describing the incisor relationship to maxilla and mandible. They concluded that most of the measurements are better descriptors of other relationships that could confound interpretation of relationships to the supporting bones.

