- American Orthodontics Molar bands/tubes.

D] Outcomes

[figure not shown]
Primary outcome: is to monitor the rate of space closure during en-masse retraction. All outcomes will be assessed as the difference between T0 at the start of retraction and T1 after complete space closure.

Secondary outcomes: is to monitor the changes in the anterior teeth position (torque and vertical position), molar rotation, anchorage loss, and pain associated with the different methods used for retraction.

E] Participant timeline:

1. The principle investigator will screen the potential patients through careful clinical examination of patients at the orthodontic department, Faculty of Oral and Dental Medicine, Future University.
2. All recruited patients should fulfil the previously mentioned inclusion and exclusion criteria.
3. Every participant will be asked to sign an informed consent before the beginning of the study.
4. After patient's enrolment, each participant will be asked for pre-intervention records to ensure proper diagnosis.

5. The principle investigator will randomly allocate the patients to one of the intervention groups.
6. Anchorage will be secured by placement of miniscrew, followed by extraction of the first premolar.
7. Active intervention will begin after proper levelling and alignment of the upper arch.
8. The principle investigator will take pre-retraction records for every participant T0.
9. In Friction mechanics group, Power chain is used for anterior segment retraction while in Frictionless group, T-loop is used for retraction.
10. Each patient will come every 4 weeks for follow up visit, for appliance activation and uptake of impression for interim records.
11. After complete space closure, the principle investigator will take post-retraction records for each participant T1.
12. Every patient will fill up a questionnaire regarding his experience during treatment.
13. The principle investigator will continue the normal treatment and achieve proper finishing for every patient after the end of the study.

E] Sample size calculation:

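### Pre/post significance tests inside each arm do not answer the randomised question, and no between-arm estimate with a confidence interval is planned

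*Combined protocol and SAP*

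**What the plan says.** The design is two independent arms: "This is a randomized clinical trial with two arms parallel group, and 1:1 allocation ratio" (Study design). The null hypothesis (Objectives of the study) and the sample size calculation both concern the difference between the two techniques.

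The Statistical Analysis section (III, C) then lists:

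- Item 1, the summaries: "Presenting the data as mean, standard deviation (SD) and Standard error (SE) values".
- Item 2, first half, the comparison of arms: "Using Paired t-test to compare between the friction and the frictionless group of retraction".
- Item 2, second half, a further use of the same test: "as well as to compare between the pre-and post -treatment data for each group".
- Item 3, for the rate: "Using Anova test to determine the rate of anterior segment retraction". No factors or contrast are given.
- The significance bullet sets P ≤ 0.05 and adds a second tier: "Highly significant variables are detected when P value is less than 0.01".

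The Outcomes section (I, D) fixes the time points: "All outcomes will be assessed as the difference between T0 at the start of retraction and T1 after complete space closure".

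Nowhere do the documents plan a between-arm mean difference, a confidence interval or any other effect estimate. Nor do they say that the within-arm results are descriptive only, or how a non-significant comparison will be read.

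**The concern.** A within-arm test asks whether teeth moved under one technique. The trial asks whether they moved differently under two. The first question is either trivial or beside the point:

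- **Extraction space.** T1 is the visit at which the space has closed, so the pre/post change is the whole space in both arms. The test must be significant in each and says nothing about which technique was faster.
- **Anchorage loss, molar rotation, torque and vertical position.** Changes may be small, so one arm can fall below 0.05 and the other above it by chance. With labels attached to each P value, that pattern can be taken for a technique effect.

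The missing estimate matters separately. With 10 to 15 patients per arm, a P value above 0.05 does not show which differences remain plausible. Only an interval for the difference does, and none is planned.

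**Working it through.** **Inputs.** From the sample size calculation: SD 0.76, difference 1.0 (no unit for either), alpha 0.05, power 0.8, 10 per arm before dropout, 15 per arm recruited. Two-sided testing is assumed, because the null hypothesis is one of equal means. The documents give no SD of change for the four tooth-position outcomes, so 0.76 is used for them as an assumption.

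**1. The plan's own figure.** n per arm = 2 × [0.76 × (1.960 + 0.842) / 1.0]² = 9.07, rounded up to 10. The stated 10 per arm reproduces. Exact two-sample t power for a difference of 1.0 is 79.5% at 10 per arm and 93.5% at 15. This is an independent-groups calculation, so the plan's sizing already assumes the unpaired comparison.

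**2. Chance that exactly one arm is significant when both truly change equally.** Let p be the power of the within-arm paired test. The arms are independent, so the chance is 2p(1−p). It peaks at 50% when p = 0.5, whatever the SD. Here p comes from the noncentral t with n−1 degrees of freedom and noncentrality δ / (0.76/√n), where δ is the common true change.

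| n per arm | True change δ | p | 2p(1−p) |
|---|---|---|---|
| 15 | 0 | 0.050 | 9.5% |
| 15 | 0.2 | 0.158 | 27% |
| 15 | 0.4 | 0.475 | 50% |
| 15 | 0.5 | 0.659 | 45% |
| 15 | 0.75 | 0.944 | 11% |
| 15 | 1.0 | 0.997 | 0.6% |
| 10 | 0.5 | 0.459 | 50% |
| 10 | 0.75 | 0.793 | 33% |
| 10 | 1.0 | 0.958 | 8% |

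Simulation (100,000 runs each) at n = 15 with δ = 0.4 and 0.5, and at n = 10 with δ = 0.5, gave 49.9%, 44.9% and 49.5%. In the same runs an independent-samples test between the arms was significant in 4.9% to 5.1%, as it should be when there is no difference.

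**3. What an interval would show.** SE of the difference = 0.76 × √(2/n): 0.278 at 15 per arm and 0.340 at 10. The 95% half-width is t(0.975, 2n−2) times this:

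- 15 per arm: 2.048 × 0.278 = 0.57
- 10 per arm: 2.101 × 0.340 = 0.71

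Three non-significant results then read differently:

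- Observed difference 0, 15 per arm: −0.57 to 0.57, which excludes the planned 1.0.
- Observed difference 0, 10 per arm: −0.71 to 0.71, which also excludes 1.0.
- Observed difference 0.5, 15 per arm: −0.07 to 1.07, which includes 1.0.

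Power for a true difference of 0.5 is 41% at 15 per arm and 29% at 10, so a non-significant result is likely even when half the planned difference is real.

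**The case against.** Several stronger readings are tempting, and the documents do not support them.

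- **That the plan judges the techniques by comparing within-arm P values.** It does not say so. Item 2 begins with a comparison of the arms, and the hypothesis and sample size are between-arm. The misreading is a risk left open. Nor does any text say that a non-significant rate result will be reported as equality.
- **That the authors have this habit.** The literature review summarises the study behind the sample size with "Moreover, a significant incisors intrusion in PG group and a significant increase in deep bite in coil spring group", which sets separate group results side by side. But this is a summary of another trial, it does not say which tests were used, and other summaries in the same review are directly comparative. It is not evidence of how this trial will be read.
- **That the primary outcome could be significant in one arm only.** For space closure both arms will be significant, so the one-arm-only pattern cannot arise there.
- **That the false-signal rate is 50%.** That is a ceiling, reached only when within-arm power is near one half. It falls below 1% at a true change of 1.0 with 15 per arm and the assumed SD.
- **That SEs will be given per arm and nothing else.** Item 1 does not say which quantities it covers. Per-arm reporting is the natural reading but an inference, and a reader given mean, SD and n by arm could derive the difference.
- **That a null result would be uninformative.** One centred on zero would exclude 1.0 at either sample size.

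After these concessions, two facts stand: tests that do not address the randomised question are written into the plan, and the estimate that does address it is absent.

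**Conclusion.** The point holds as a low-cost improvement to the analysis section. It does not show that the trial will reach a wrong conclusion.

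The within-arm tests are uninformative for space closure and open to misreading for four secondary outcomes. The size of that risk is at most 50% per outcome under equal true change. At 15 per arm it runs from about 50% (true change 0.4) through 11% (0.75) to 0.6% (1.0). Those three figures rest on an SD of change of 0.76, which the documents do not give for these outcomes. The ceiling does not depend on it.

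The interval half-widths of 0.57 and 0.71 rest on the plan's SD applying to the rate, in a unit the sample size calculation does not state.

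Naming a paired test for independent arms is a defect in its own right. It matters here because a between-arm interval needs a method that fits the design.

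**What to change.** In the Statistical Analysis section:

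1. Replace the within-arm tests in item 2 with a descriptive table of T0 to T1 changes by arm (mean and SD), without P values or significance labels.
2. For every outcome, report the between-arm difference (in rate, or in T0 to T1 change where that applies) with its 95% CI from an independent-samples or baseline-adjusted analysis, not a paired test.
3. State that a non-significant rate result will be interpreted from its CI and not taken as equality. Give the unit of the planned difference of 1.0, so that the interval can be set against it.

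The cost is wording only. Sample size, visits and measurements are unchanged. The downside is that per-arm and secondary results lose their *significant* and *highly significant* labels.
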